## 2.3 STUDY DRUG

The drug to be administered is urea (brand name Ure-Na™). Urea is a medical food or dietary supplement considered by the FDA under the GRAS (Generally Regarded As Safe) category. Patients will be instructed to start urea at a dose of 15 g once daily. Dose titration then will occur based on the absolute increase in PNa on days 7 and 14 as follows:

- Day 7: If PNa increases ≥3 mmol/L from baseline, then continue same urea dose. If PNa increases <3 mmol/L from baseline, then increase urea to next dose.
- Day 14: If PNa increases ≥ 6 mmol/L from baseline, or PNa increases <6 mmol/L from baseline and PNa ≥135 mmol/ L, then continue same urea dose. If PNa increases <6 mmol/L from baseline and PNa <135 mmo/L, then increase urea to next dose.

The dosing scheme for urea will involve increasing when appropriate, from the starting dose of 15 g/day, to 30 g/day in 2 divided doses, and subsequently, when appropriate, from 30 g/day to 60 g/day (in 2 divided doses). The maximal dose of urea administered will be 60 g/day. The route of administration will be oral and the total duration of administration will be  $42 \pm 3$  days.

Oral urea use is occasionally associated with the onset of nausea, vomiting, diarrhea and headaches. If these symptoms appear then they will be initially managed by asking patients to monitor their symptoms and report to the research coordinator if symptoms persist after

24h. If symptoms persist, urea dose will be reduced by 50%. If symptoms persist 72h after reducing the dose of urea, urea will be discontinued.

Subjects will be seen at the UPMC kidney clinic immediately after the completion of their participation in the study for consideration of continuation of urea therapy.

### 2.3.1. Study Drug Preparation and Dispensing

The study drug will be donated by Nephcentric, the manufacturer of Ure-Na™. Ure-Na™ is formulated as a powder packaged in a 21-g pouch or sachet. Each pouch of Ure-Na™ contains 15 g of pharmaceutical grade urea and 6 g of other ingredients including natural flavors, citric acid, maltodextrin, calcium silicate, and sucralose. The powder is then mixed with 3 to 4 oz. of water or juice for oral consumption. No on-site preparation of the study drug will be performed. Patients will be given 6 boxes of Ure-Na™ each containing eight pouches (total of 48 pouches) and instructed to take the study drug at home as indicated. Some more pouches of Ure-Na™ will be given at day 14 as necessary to complete their participation in the study.

### 2.3.2. Drug Administration

During the study visit at day 0, patients will be given six boxes of Ure-Na™ each containing eight pouches (total of 48 pouches) to take home. Some more pouches of Ure-Na™ will be given at day 14 as necessary to complete their participation in the study. Subjects will be instructed to take 1 pouch (15 g of urea) per mouth once daily. Subjects will be instructed to carefully open the pouch, pour all the content of the pouch into a glass or cup, add 3 to 4 oz of water, stir, and drink after a meal to decrease gastrointestinal intolerance. Subjects will be told that the dose of urea will be titrated throughout the study based on plasma sodium levels and/or the appearance of side effects and this will be communicated during the study assessments by the research coordinator. In addition, subjects will be instructed to store the study drug at home at room temperature, in a dry place, out of direct sun-light.

#### 2.3.3. Dose Selection

Urea, also known as Carbamide, it is an organic compound with formula  $CH_4N_2O$ . This amide has two amino groups (-NH2) joined by a carbonyl (C=O) functional group. Urea is an endogenous product of protein and amino acid catabolism. Oral urea works as an osmotic diuretic that increases urinary water excretion and has been available for use in Europe for the treatment of hyponatremia for many years. Preliminary evidence of the potential efficacy of urea derives from small European case series.(1) Decaux et al.(3) studied 7 patients with chronic hyponatremia and found that treatment with urea over a period of up to 9 months resulted in an increase in mean PNa from 116 to 136 mmol/L and was not associated with any major side effects. Another study by Decaux et al.(27) of 50 patients with mild to moderate hyponatremia (PNa 120 to 134 mmol/L) found that 2 days of treatment with urea increased PNa by 7±4 mmol/L. Collectively, these and other small studies demonstrated that urea increases PNa. However, these studies were retrospective, lacked a control group, included small numbers of patients, used a formulation of urea that is not available in the United States, and did not examine whether the effect of urea on raising PNa translates into a reduction in morbidity and/or mortality. In 2016, Ure-Na™, a novel formulation of oral urea became available in the United States. The FDA considers urea to be a medical food, and therefore, does not

require a medical prescription for its use. Our group published the first study on the efficacy of this agent for the treatment of hyponatremia in the United States.(4) We identified patients hospitalized at UPMC with PNa <135 mmol/L who received urea, including a subgroup with SIADH who received urea as the sole drug therapy for hyponatremia ('urea-only' patients). Overall, 58 patients received urea (7.5-90 g/day) over a median of 4.5 days and demonstrated an increase in PNa from 124 to 131 mmol/L (p<0.001). Among 12 'urea-only' treated patients, PNa increased from 125 to 131 mmol/L (p=0.001) with a larger increase in PNa by 24 h (2.5 mmol/L [IQR 0-4.5] vs. -0.5 mmol/L [IQR -2.5 to 1.5], p=0.04) and more patients normalized PNa (33% vs. 8%, p=0.08) compared to a control group. No patients experienced overly rapid correction of PNa and no serious adverse events were reported. While our study was retrospective and limited to hospitalized patients, the findings support the potential efficacy and safety of this agent. After the publication of our study, two other observational studies were published supporting the efficacy, safety, and tolerability of oral urea in hyponatremia. (28, 29) Just one past study compared urea to other therapies for hyponatremia. Soupart et al. compared urea to vasopressin antagonists in 13 patients with chronic SIADH.(30) Patients were treated with vaptans (satavaptan and tolvaptan) for 1 year, during which PNa increased from 125±3 mmol/L to 135±3 mmol/L. Vaptans were then discontinued, leading to recurrent hyponatremia. After an 8-day washout period, oral urea was prescribed for 1 year with normalization of PNa in all patients (mean PNa 135±2 mmol/L). Patients tolerated urea well with no significant side effects. To date, there have been no studies comparing urea to fluid restriction.

Our study propose to use the oral route for urea administration. Pharmacological urea currently exist in topical and oral formulations. The oral formulation allows for systemic absorption and renal excretion causing the desired pharmacological effect (i.e. osmotic diuresis). The initial dose of urea to be administered during our study will be 15 g/day but this can be titrated in subsequent study visits based on efficacy and safety. The next dose in our titration algorithm is 30 g/day (in 2 divided doses), and the next and maximal dose allowed will be 60 g day (in 2 divided doses). The European Clinical practice guideline on diagnosis and treatment of hyponatraemia(26) recommended a urea dose of 0.25 - 0.5 g/kg/day which for a 60 kg person constitutes between 15 and 30 g of urea per day. Our study using Ure-Na™ at the University of Pittsburgh Medical Center(4) showed that patients were treated with doses ranging from 7.5 g/day up to 90 g/day. however most patients required doses between 15 and 30 g. The rationale behind the divided doses with doses of 30 or 60 g/day of urea is double. Urea's half-life is 2.5 h and a single dose of urea is completely eliminated via the kidneys within 12 h. Also, higher doses of urea are more likely to cause gastrointestinal side effects. Therefore, to achieve a sustained effect while minimizing adverse reactions a twice daily dose of urea will be more appropriate. While past observational studies demonstrated a potential benefit of increasing plasma sodium on neurocognitive outcomes within 1 week (8, 32, 33), we have increased the treatment duration to 42 ± 3 days to ensure a longer period of plasma sodium normalization that captures the potential beneficial effects of urea on these outcomes.

For a summary of the information related to the human pharmacokinetics and human safety profile of urea, as well as findings from non-clinical studies that support the evaluation of urea in humans, please, refer to: *Toxicological Review of Urea by the United Stated Environmental Protection Agency (EPA).* 

#### 2.3.4. Treatment Period

42 ± 3 days

### 2.3.5. Breaking the Blind

The proposed clinical study will not be blinded.

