# **1.4 SIGNIFICANCE**

By demonstrating the feasibility of recruiting patients, documenting patient adherence, and establishing a signal of efficacy to increase PNa and potentially improve neurocognitive function and postural control and stability, this pilot study will generate the data needed to justify and

inform the design of an adequately powered, multi-center, randomized, placebo-controlled clinical trial to investigate whether therapy with urea decreases morbidity, mortality, and costs. This proposal will bring together a multi-disciplinary group of investigators with expertise in the diagnosis and treatment of hyponatremia (Drs. [name] and [name]), assessment of neurocognition and posture control/stability ([name] and [name]), clinical trial design and implementation (Drs. [name] and [name]), and biostatistics ([name]). Establishing a track record of collaboration among this group of investigators will greatly strengthen future efforts to extend this line of investigation to a much larger numbers of patients. Assuming that as many as 1.2% of the overall adult population has chronic hyponatremia and that half or more of these patients could be treated with urea, as many as 2 million patients nationwide could

ultimately benefit from this novel and inexpensive intervention.

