- A co-investigator will test patients' balance while standing on a specialized piece of equipment. Patient will be asked to stand on both legs on top of a platform in a dynamic moving environment. Patient will go through six conditions, with three trials per condition, lasting about 20 seconds each. Patient will be asked to look forward, and stand as motionless as possible with your arms at your sides. The six conditions include the possibility of moving surroundings or moving base of support. If patient move or lose his/her balance during the procedures, patient will be asked to repeat that part again. Patient will be supported by means of a harness in the equipment to make sure he/she cannot fall over while performing the tests.
- The research coordinator will instruct the patient to restrict his/her fluid intake to no more 1200 mL/day for the next 42 ± 3 days. The research coordinator will provide the patient with a diary to record daily fluid intake.
- Patients will be randomized prior to or at the first study visit (Period 1 Day 0) following completion of baseline assessments. Our biostatistician will generate the randomization list using permuted blocks of random block sizes of 4 and 6 and our systems analyst will load the list into RedCAP. To preserve allocation concealment for consecutively enrolled participants, we will use the randomization module in RedCAP to assign each participant 1:1 to either On-to-Off Urea sequence or Off-to-On Urea sequence.
- If patient is randomized to take On-to-Off Urea sequence then the research coordinator will give the patient 48 urea powder pouches with instructions on how to take the urea every day. The research coordinator will provide the patient with a diary to record patient's daily urea intake.
- This visit will last approximately 2.5 hours.

Second study visit (Day 7 of Period 1)

- The research coordinator will call the patient on the phone to ask some questions about any new symptoms patient might have experienced since his/her last visit.
- The research coordinator will direct the patient to go the UPMC clinical laboratory of the patient's choice that day to have his blood drawn for analysis of a basic metabolic panel.
- If patient is taking urea, we might call the participant on the phone again to ask to change the dose of urea depending on the sodium level results.
- This visit will last approximately 20 minutes.

Third study visit (Day 14 of Period 1)

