- The research coordinator will call the patient on the phone to ask some questions about any new symptoms patient might have experienced since his/her last visit.
- The research coordinator will direct the patient to go the UPMC clinical laboratory of the patient's choice that day to have his blood drawn for analysis of a basic metabolic panel.
- The research coordinator will instruct the patient to bring his fluid and urea intake diaries to the next study visit.
- The research coordinator will give or mail the patient a container with instructions to collect urine for 24 hours prior to next study visit.
- If patient is taking urea then research coordinator will give and/or mail the patient enough urea powder pouches to complete his/her participation in this period of the study.
- If patient is taking urea, we might call the participant on the phone to ask to change the dose of urea depending on the sodium level results.
- If urea dose is adjusted to less than the maximum allowed dose, research coordinator will direct the patient to go the UPMC clinical laboratory of the patient's choice in approximately 7 days to have his/her blood drawn for analysis of a basic metabolic panel.
- This visit will last approximately 30 minutes.

Reminder telephone call

• The research coordinator will call the patient on the phone 48-72 hours before the next study visit to remind him/her of the upcoming study visit.

Fourth study visit (Day 42 of Period 1)

- Patient will come in person to the University of Pittsburgh Neuromuscular Research Laboratory located at [name].
- The research coordinator will collect the patient's fluid and urea intake diaries.
- The research coordinator will ask the patient some questions about any new symptoms patient might have experienced since his/her last visit.
- If patient is taking urea then the research coordinator will ask patient some questions related to acceptability of urea.
- Patient will bring the container with the 24-hour urine collection he/she started the day prior. The research coordinator will send the specimen promptly to the UPMC Presbyterian clinical laboratory for processing and analysis of the following: creatinine, urea nitrogen, uric acid, osmolality, sodium, and potassium

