- The research coordinator will draw approximately 14 mL of patient's blood and send the specimen promptly to the UPMC Presbyterian clinical laboratory for processing and analysis of the following: basic metabolic panel, plasma osmolality, and plasma uric acid.
- Patient will complete the SF-12 survey with pen and paper.
- A co-investigator will test patients' reactions and decision making using specialized software on a tablet computer.
- A co-investigator will test patients' balance while standing on a specialized piece of equipment. Patient will be asked to stand on both legs on top of a platform in a dynamic moving environment. Patient will go through six conditions, with three trials per condition, lasting about 20 seconds each. Patient will be asked to look forward, and stand as motionless as possible with your arms at your sides. The six conditions

include the possibility of moving surroundings or moving base of support. If patient move or lose his/her balance during the procedures, patient will be asked to repeat that part again. Patient will be supported by means of a harness in the equipment to make sure he/she cannot fall over while performing the tests.

- The research coordinator will ask patient to stop fluid restriction.
- If patient is taking urea then the research coordinator will instruct the patient to stop taking urea and return all the urea pouches he/she did not use to the research coordinator.
- The research coordinator will provide the patient with a container with instructions to collect urine for 24 hours prior to next study visit.
- This visit will last approximately 2.5 hours.

Reminder telephone call

• The research coordinator will call the patient on the phone 48-72 hours before the next study visit to remind him/her of the upcoming study visit.

Fifth study visit (Day 0 of Period 2)

- Patient will come in person to the University of Pittsburgh Neuromuscular Research Laboratory located at [name].
- Patient will bring the container with the 24-hour urine collection he/she started the day prior. The research coordinator will send the specimen promptly to the UPMC Presbyterian clinical laboratory for processing and analysis of the following: creatinine, urea nitrogen, uric acid, osmolality, sodium, and potassium.

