#### 2.5.3 Efficacy Analysis

This study is not powered to establish the efficacy of urea on increasing PNa or improving neurocognition and/or postural control/stability. However, to justify a future large, randomized clinical trial of urea, we need proof of concept data that urea has potential benefits for these outcomes. We will summarize patient demographics and clinical characteristics by study group. For the primary outcomes (PNa, neurocognition scores, postural control/stability scores) and secondary exploratory outcome (SF-12 scores), we will calculate change from baseline to day 42 in each treatment period. We will analyze these data using a linear mixed effects model with patient-specific random effects to account for within-patient correlations. Model predictors will include treatment,

period and treatment period interaction. Coefficients and 95% CIs will be used to quantify the treatment effect. We will also use this model to assess period effect and carryover effects (treatment period interaction).

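### The testers behind nine of the ten primary efficacy outcomes could be masked cheaply, because testing and urea handling already sit with different roles

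*Combined protocol and SAP*

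**What the plan says.** Section 2.3.5 is one sentence: "The proposed clinical study will not be blinded". It gives no reason and does not distinguish patients, coordinator and testers.

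The visit descriptions in section 2.2 (Research activities) divide the work by role. At day 0 and day 42 of both periods, "A co-investigator will test patients' reactions and decision making using specialized software on a tablet computer" and "A co-investigator will test patients' balance while standing on a specialized piece of equipment". Urea is handled by someone else. At the start of the urea period "the research coordinator will give the patient 48 urea powder pouches with instructions on how to take the urea every day", and at its end "the research coordinator will instruct the patient to stop taking urea and return all the urea pouches he/she did not use". At day 42, "The research coordinator will collect the patient's fluid and urea intake diaries", and the same person asks about acceptability if the patient is on urea.

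Section 1.4 lists the investigators responsible for "assessment of neurocognition and posture control/stability" apart from those responsible for hyponatremia. Section 2.5.3 names the neurocognition and postural scores as primary outcomes alongside plasma sodium.

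**The concern.** The control periods have no placebo, and section 1.2 predicts better neurocognitive and postural scores on urea. A tester who shares that expectation and knows the period can, without intending to, give more help or more repeat attempts in the urea period. The crossover removes stable differences between patients. It does not remove a tester effect that follows treatment, because that effect sits in the same within-patient contrast as the drug effect. Sections 1.4 and 2.5.3 say the results are meant to justify a larger trial, so a false signal would have a cost. Open-label treatment does not by itself require open assessment, and the role split makes masked assessment practical here.

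**Working it through.** **1. Outcomes that pass through a tester.** Items 6 to 15 of the primary endpoints in the synopsis are the efficacy changes: 15 − 6 + 1 = 10. Item 6 is plasma sodium, a laboratory value. Items 7 to 15 are performance tests: one from PACT, one from the Senaptec battery, one from the force plate and six from dynamic stance testing. That is nine of ten.

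**2. Tasks side by side (section 2.2, test visits).**

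| Task | Role |
|---|---|
| Neurocognitive and balance tests, days 0 and 42, both periods | Co-investigator |
| Handing out and taking back urea | Research coordinator |
| Day 7 and day 14 calls | Research coordinator |
| Diaries and acceptability questions | Research coordinator |

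No testing task as described needs the period assignment. Titration follows plasma sodium (section 2.3).

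**3. Tasks are separated, but information is not.** The text leaves these routes open:
- Section 2.2, first study visit: randomization may happen before or at that visit, so possibly before baseline testing.
- Section 2.2, day 42 visits: diary collection and acceptability questions are listed before testing, at the same laboratory visit.
- Section 2.3.7: listed co-investigators may prescribe urea, and testers are not excepted.
- Sections 2.3.6 and 10: withdrawal is agreed by, or discussed with, all team members.
- Section 9.4: sub-investigators join the four-weekly team meetings.

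With two sequences, a tester who learns the treatment in one period knows it for the other.

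**4. Room for tester influence (section 2.2 and appendix).** Repeating a part when the patient moves or loses balance is described only for the six-condition balance procedure, which matches the Sensory Organization Test. Reaction time has automated instructions, computed averages and a fixed outlier rule. Dynamic visual acuity uses a staircase algorithm. The NeuroCom tests use the manufacturer's verbal cues. Encouragement is mentioned only for guessing in one subtest. What remains is delivery of instructions, informal encouragement on effort-dependent tasks, and the repeat rule.

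**5. Illustration of size.** The documents give no bias figure, so b = 0.1 to 0.2 SD of the within-patient difference is an assumption. The endpoint contrast is (ON day 42 − ON day 0) − (OFF day 42 − OFF day 0). A shift of b in ON day 42 alone moves the contrast by b. If ON day 0 is shifted in the same direction, part of it cancels.

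For a two-sided 5% paired t test with no true effect, noncentrality is b√n with n − 1 degrees of freedom:

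| n | b | b√n | Chance of nominal significance |
|---|---|---|---|
| 30 | 0 | 0 | 5% |
| 30 | 0.1 | 0.548 | 8.3% |
| 30 | 0.2 | 1.095 | 18.5% |
| 24 | 0.1 | 0.490 | 7.6% |
| 24 | 0.2 | 0.980 | 15.6% |

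The rows with n = 24 = 0.8 × 30 allow for one patient in five not being evaluable.

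**6. Relation to the planned effect.** Section 2.5.1 gives 83% power for a standardized difference of 0.65 but does not say which SD is meant. On the SD of the within-patient difference, 30 patients give 93.1%, and 22 evaluable patients give 82.8%. On the between-patient SD with a within-patient correlation of 0.3, the effect is 0.65/√(2 × 0.7) = 0.549 and 30 patients give 82.7%. The 83% can be reached, but only with an unstated assumption. The illustrative bias is then 0.1/0.65 = 15% to 0.2/0.65 = 31% of the target on the first scale, or 0.1/0.549 = 18% to 0.2/0.549 = 36% on the second. Masking testers changes neither the sample size nor the power.

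**The case against.** The strongest reply is that this is a declared open-label pilot, not powered for efficacy, with largely device-scored tests and patients who know what they are taking. Masking testers leaves patient expectation untouched, and on effort-dependent tests that may be the larger bias. Some patients will also reveal their treatment. All of this stands. It limits the benefit and is why the point is an improvement only.

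A second reply is that masking is not free: several procedures must change, and hiding the allocation field alone would leave the routes in step 3 of the working open. This also stands. A reader might infer from the role split that testers are already nearly masked, or that nothing further is needed. The documents do not support that.

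A reader might also infer that all nine outcomes rest on a tester's judgement. They do not: the only repeat decision described belongs to one balance procedure, and scoring is mostly automatic. What survives is narrower. A source of bias that could be reduced is left open on primary outcomes, and section 2.3.5 gives no reason for it.

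**Conclusion.** The point holds as a cheap improvement with partial benefit. The absence of tester masking and the division of roles are both plain in the text. That no new staff role is needed is an inference from that division; the documents do not say so.

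The likely effect of tester bias may be modest. The 0.1 to 0.2 SD range, and the 8.3% and 18.5% that follow from it with 30 patients, rest on an assumed bias confined to day 42 on urea, an assumed two-sided 5% test and a simple paired analysis. They show sensitivity and do not estimate what will happen.

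Two stronger readings are tempting. One is that section 2.3.5 is an error or contradicts the rest of the protocol. It does not, since open assessment is a permitted choice. The other is that the efficacy estimates will be biased by a known share of the planned effect. The documents give neither a bias size nor the SD scale of the 0.65. Plasma sodium is unaffected as a laboratory value.

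**What to change.** In section 2.3.5, state that treatment is open-label for patients and coordinator, but that the co-investigators who run PACT, Senaptec, the force plate and NeuroCom are kept unaware of sequence and period. To make that workable:

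- Randomize only after Period 1 day 0 testing is complete.
- Hide the REDCap allocation from testers.
- Handle pouches, diaries and acceptability questions away from the test room.
- Ask patients not to disclose their treatment to the tester.
- Keep testers off the urea prescriber list.
- Keep participant-level treatment status out of what testers see and hear at the four-weekly meetings.
- Exempt testers from withdrawal consultations and adjust the all-members wording in sections 2.3.6 and 10. The withdrawal criteria themselves are not at issue.
- Record the tester's guess of treatment at each day 42 session, so that the report can show how far masking held.

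The cost is protocol wording, one access setting, one case report form item and a small procedural burden at visits and meetings. Masking will be partial and patient expectation remains, which the report should say. If the sponsor prefers open assessment, section 2.3.5 should give the reason.
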